6.3.4 Point of Enrolment

The point of enrolment corresponds to the time at which a patient signs and dates his/her consent form. Patients are to be enrolled at about 6 investigational sites in EU.

6.3.5 Point of Randomisation

Not Applicable

6.3.6 Total Expected Duration of the Clinical Investigation

This clinical investigation is planned to start in August 2023 and to be completed in January 2024.

6.3.7 Expected Duration of each Patient's Participation

The treatment period for each patient is 36 + 3 days for a total maximum investigation duration of 39 days.

6.3.8 Number of Patients Required to be Included in the Clinical Investigation

A total of **CC1** patients should be included in order to have **CC1** evaluable patients in the FAS population.

Evaluable patients will be defined as included patients having received at least one dose of IMD.

6.3.9 Estimated Time Needed to Select this Number (*i.e.* enrolment period)

The enrolment period is estimated at about 4 months.

6.3.10 Relationship of Investigation Population to Target Population

As per IFU, the target population of the medical device is adults with dry eyes, including wearers on any type of contact lenses.

The purpose of the clinical investigation is to evaluate the safety and performance of T2769 treatment in adults, wearing any type of contact lens and who experience symptoms of dry eye and discomfort during lens wear.

Thus, the contact lens wearers population is part of the target population.

6.3.11 Information on Vulnerable, Pregnant, and Breastfeeding Population

This clinical investigation will not be conducted in vulnerable populations as children, pregnant or breastfeeding women. See Section 15.

6.4 PROCEDURES

Timing of procedures is presented in **Table 2 Schedule of Visits and Procedures**.

Some procedures must be performed by the same investigator or the same authorized assessor/delegate throughout the clinical investigation (BCVA, slit lamp examination, Schirmer test, tolerance/performance assessment by investigator).

6.4.1 Description of all the Clinical-Investigation-Related Procedures that Patients Undergo during the Clinical Investigation.

6.4.1.1 Demographics and Screening/Inclusion Characteristics

The following characteristics will be collected:

- Age (in years),
- Gender,
- Previous and concomitant ocular and non-ocular medications (see 6.4.1.4),
- Result of the urinary pregnancy test,
- Contact lens history:
 - o contact lens type,
 - o mean contact lens wearing time over the month preceding inclusion (hours/day and days/week),
 - o cleaning solution type (preserved or not preserved),
 - o history of contact lens intolerance.
- Ocular medical and surgical history with relevant diagnosis (including dry eye),
- Systemic medical and surgical history with relevant diagnosis.

6.4.1.2 Performance Measures

6.4.1.2.1 CLDEQ-8 self-questionnaire CCI

The CLDEQ-8 questionnaire (Copyright© Begley & Chalmers 2016, all rights reserved) must be completed by the patient at each visit. It consists of 8 questions designed to measure dry eye symptoms specifically related to the use of contact lenses. The total score is obtained by adding the scores obtained for each answer. The final score is ranging from 1 to 37.

6.4.1.2.2 Soothing sensation

Patient will be asked: "How would you rate your soothing sensation just after (less than 5 minutes) study treatment instillation(s)?

The soothing sensation felt by the patient just after (less than 5 minutes) IMD instillation after 15 and 36 days of treatment will be assessed according to the following scale:

- (0) = None
- (1) = Mild
- (2) = Moderate
- (3) = Important

The soothing sensation will be assessed in global for both eyes at each post-baseline visit.

6.4.1.2.3 *Ocular Surface Disease Index (OSDI) self-questionnaire*

The OSDI questionnaire (Schiffman et al., 2000; Miller et al., 2010) must be completed by the patient at the beginning of each visit before medical history information is collected or any investigation assessments are performed. The total OSDI score range on a scale from 0 to 100.

CCI

6.4.1.2.4 *Ocular discomfort (VAS)*

Ocular discomfort (global evaluation for both eyes) will be assessed by the patient at D1, D15 and D36 visits according to the following:

“Please mark a vertical line on the horizontal line, indicating your level of ocular discomfort due to ocular dryness within the last 48 hours”. VAS will be a 100 mm line: 0 mm = No discomfort, 100 mm = Maximal discomfort.

6.4.1.2.5 *Ocular symptoms throughout the day*

CCI

This section is completely redacted by a large black box.

6.4.1.2.6 *Daily contact lens wearing time*

CCI

6.4.1.2.7 *Slit lamp examination*

- Conjunctival hyperaemia

CCI

- Tear Break-Up Time (TBUT)

The tear film stability will be measured 3 times after the instillation of fluorescein. TBUT will be rapidly assessed and expressed in seconds. The sum of the 3 measures will also be expressed in seconds. TBUT will be measured in each eye and at each visit.

- Total ocular surface staining (Oxford scale)

The total ocular staining grade using Oxford 0-15 grading scheme will be assessed at each visit by staining in corneal area and conjunctival areas (temporal and nasal) by fluorescein with a yellow filter.

Cornea and conjunctiva staining is represented by punctate dots on a serie of panels (A-E). Staining ranges form 0-5 for each zone and from 0-15 for the total exposed inter-palpebral conjunctiva and cornea. The dots are ordered on the log scale (Oxford scale) CCI

The score for each area will be recorded for each eye. The global score (sum of score reported for each area: corneal + conjunctival) will be used for statistical analysis.

6.4.1.2.8 *Schirmer Test*

CCI

6.4.1.2.9 *Performance Assessment by the investigator*

The investigator must answer to the following question at the end of the patient examination at D15 and D36:

“Do you consider the IMD performance as:

- Very satisfactory
- Satisfactory
- Not very satisfactory
- Unsatisfactory”

6.4.1.3 *Safety measures***6.4.1.3.1** *Visual acuity*

Far BCVA will be assessed in each eye at D1 and D36 using the same chart (for example a Snellen chart) throughout the clinical investigation. It can be expressed using units as /10, decimal notation, MAR, logMAR or Snellen notation. It will be analysed after conversion in LogMar. **CCI**

6.4.1.3.2 *Adverse Events*

Ocular and systemic AEs will be collected by the investigator (or authorised assessor/delegate) at each visit.

In case of appearance of a new clinically significant sign or symptom, it should be reported as an AE or SAE.

In case of clinically significant worsening of a pre-existing sign or symptom, it should be reported as an AE or SAE.

The handling of AEs is detailed in Section 14.

6.4.1.3.3 *Device deficiencies*

Device deficiencies will be collected by the investigator (or authorised assessor/delegate) at each visit.

6.4.1.3.4 *Ocular Tolerance Assessment by the patient*

The investigator must ask the patient the following question in local language:

“How do you consider the study treatment ocular tolerance?

- Very satisfactory
- Satisfactory
- Not very satisfactory
- Unsatisfactory”

6.4.1.3.5 *Ocular Tolerance Assessment by the investigator*

The investigator must answer to the following question in local language:

“How do you consider the IMD ocular tolerance?

- Very satisfactory
- Satisfactory
- Not very satisfactory
- Unsatisfactory”

6.4.1.3.6 *Treatment Compliance Evaluation*

Patient will return all investigation products (IMD), whether used or unused.

For IMD (T2769), the patient will also have to report information about his/her compliance on a paper patient diary during the treatment period. Each day the patient will enter the date and

number of instillations* per day. Moreover, he/she will be asked to add the date and hour of last instillation before the beginning of each post-inclusion visit.

In addition, compliance will be assessed by questioning the patient during the visit (e.g. if there was any treatment interruption or missed instillation) and by checking the paper patient diary.

* one instillation = 1 drop in each eye

6.4.1.4 *Prior and Concomitant Therapy*

At inclusion visits, patient will be asked what treatment he/she has taken within the last 3 months; this will be recorded on the e-CRF documenting product details, dose and treatment duration.

Concomitant treatment means any medications or non-medicinal therapies given concurrently with the IMD. Any other local or systemic treatment necessary for the patient's welfare has also to be recorded on the patient medical record and on the e-CRF documenting product details, dose and treatment duration. In case of premature discontinuation, the new treatment for dry eye with the start date and dosing must also be collected.

6.4.1.5 *Permitted Treatments*

Auxiliary products are permitted. See Section 6.2.2.

Systemic medication not listed in Table 1 Prohibited treatments (medications/non-medicinal therapies/procedures) are permitted **ONLY** if there has been no modification of the dosage in the month preceding the inclusion visit and if no modification is planned throughout the duration of the study.

6.4.1.6 *Prohibited Prior and Concomitant Medications or Treatments*

6.4.1.6.1 *Rescue Medications (RMs)*

Not Applicable.

6.4.1.6.2 *Prohibited Treatments other than Rescue Medications (RMs)*

Prohibited treatments as well as prohibited modifications during the clinical investigation are presented in the summary in the exclusion criteria and in Table 1 Prohibited treatments (medications/non-medicinal therapies/procedures).

6.4.2 **Description of those Activities Performed by Sponsor Representatives (excluding monitoring)**

Laboratoires THEA through Clinical Research Organisations (CROs) is responsible for selecting the investigator(s). Each investigator should be qualified by training and experience and should have adequate resources to properly conduct the clinical investigation.

Laboratoires THEA/representatives of Laboratoires THEA will remind the investigator upon his/her responsibilities and procedures for ensuring adequate and correct documentation.

Laboratoires THEA will inform the investigator, directly or through CRO in charge of monitoring, prior to the commencement of the clinical investigation of all relevant chemical, toxicological and clinical information required for the proper planning and conduct of the clinical investigation and will update this as often as may be necessary during the course of the clinical investigation. However, this obligation shall not require Laboratoires THEA to provide

information which is already available in published material or of which the investigator could reasonably be expected to have knowledge in view of his/her professional training.

Laboratoires THEA or CROs will nominate a suitably trained person or persons to monitor the clinical investigation and to liaise with the investigator.

Laboratoires THEA/representatives of Laboratoires THEA, will also be responsible for complying with the local regulations applicable to clinical investigation.

6.4.3 Any Known or Foreseeable Factors that may Compromise the Outcome of the Clinical Investigation or the Interpretation of Results

The population will be selected according to the inclusion and exclusion criteria to have a homogenous population.

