Schedule of Assessments	Please refer to the Table 2 Schedule of Visits and Procedures .

Table 2 Schedule of Visits and Procedures

	Visit#1 Inclusion Visit (D1, afternoon)	Visit#2 D15 (±1 day), afternoon ⁽¹⁾	Visit#3 Final visit ⁽¹⁾ D36 (+3 days), afternoon or premature discontinuation visit ⁽²⁾
Informed consent	X		
Demography	X		
Contact lens history	X		
Ocular and Systemic Medical and Surgical History (including dry eye)	X		
Previous and Concomitant Ocular/Non-ocular Treatments	X	X	X
CLDEQ-8 self-questionnaire ⁽³⁾	X	X	X
Soothing sensation just after (less than 5 min) IMD instillation ⁽³⁾		X	X
OSDI self-questionnaire ⁽³⁾	X	X	X
Ocular discomfort evaluation (VAS) ⁽³⁾	X	X	X
Ocular symptoms throughout the day ⁽³⁾	X	X	X
Contact lens wearing time	X	X	X
Far Best Corrected Visual Acuity (BCVA) ⁽⁴⁾	X		X
Slit Lamp Examination ⁽⁴⁾	X	X	X
Conjunctival Hyperaemia (Mc Monnies photographic scale) ⁽⁴⁾	X	X	X
TBUT ⁽⁴⁾	X	X	X
Oxford 0-15 grading scheme (corneal and conjunctival staining by fluorescein with a yellow filter) ⁽⁴⁾	X	X	X

	Visit#1 Inclusion Visit (D1, afternoon)	Visit#2 D15 (± 1 day), afternoon ⁽¹⁾	Visit#3 Final visit ⁽¹⁾ D36 (+3 days), afternoon or premature discontinuation visit ⁽²⁾
Schirmer Test (without anaesthesia) ⁽⁴⁾	X	X	X
Adverse Events		X	X
Device deficiency		X	X
Urine Pregnancy Test	X		X
Verification of Inclusion and Exclusion Criteria	X		
Ocular tolerance assessment by the patient ⁽³⁾		X	X
Ocular tolerance assessment by the investigator ⁽⁴⁾		X	X
Performance assessment by the investigator ⁽⁴⁾		X	X
Training of the patient for diary completion	X	X	
Patient diary dispensation	X	X	
IMD Dispensation	X		
IMD Compliance / Patient diary completion review		X	X
Record of used/unused IMDs (in Treatment Kit Tracking Form)			X

1) No IMD instillation at least 2 hours before visit#2 and visit#3.

2) If premature discontinuation, **also** collect the new treatment for the dry eye (if applicable) with the start date and the dosing.

3) These questionnaires and VAS must be answered by the patient at the beginning of the visit (before examination).

4) Ophthalmological examinations and assessments **MUST** be performed by the **SAME** investigator.

TABLE OF CONTENTS

1	GENERAL.....	1
1.1	Identification of the Clinical Investigation Plan (CIP)	1
1.1.1	Clinical Investigation References	1
1.1.2	CIP Amendments.....	2
1.1.3	Abbreviations and Acronyms	4
1.2	Sponsor	6

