6.1.3.2 Secondary Performance Endpoints

The secondary performance endpoints are:

- Change from baseline^a (D1) in CLDEQ-8 total score* at D15.
- Soothing sensation just after (less than 5 minutes) instillation* at D15 and D36.
- Change from baseline^a (D1) in OSDI* total score at D15 and D36.
- Change from baseline^a (D1) in the ocular discomfort score on the VAS* at D15 and D36.
- Score of each ocular symptom throughout the day* (burning/irritation, stinging/eye pain, itching/pruritus, eye dryness feeling, tearing, foreign body sensation) at D15 and D36 and change from baseline^a in the total score of these symptoms.

- Change from baseline^a (D1) in contact lens wearing time at D15 and D36.
- Change from baseline^a (D1) in conjunctival hyperaemia score at D15 and D36 separately in the studied eye^b and in the contralateral eye.
- Change from baseline^a (D1) in TBUT at D15 and D36 separately in the studied eye^b and in the contralateral eye.
- Change from baseline^a (D1) in total ocular surface staining grade according to Oxford 0-15 grading scheme at D15 and D36 separately in the studied eye^b and in the contralateral eye.
- Change from baseline^a (D1) in Schirmer test result (without anesthesia) at D15 and D36 separately in the studied eye^b and in the contralateral eye.
- Performance assessment by the investigator at D15 and D36.

^abaseline is defined as the assessment at inclusion visit before the first IMD instillation. Missing value at inclusion visit will not be replaced.

^bdefined in the statistical considerations section.

*Patient questionnaire

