6.5.1 Source Documents

Each participating investigational site will maintain appropriate medical and research records in compliance with GCP (ISO 14155 current version) and any other regulatory and institutional requirements for the protection of patient's confidentiality.

Source data are all information in original records and certified copies of original records of clinical findings, observations, or other activities in a clinical investigation necessary for the reconstruction and evaluation of the clinical investigation. Source data are contained in source documents.

Source documents are any original documents, data and records. These may include, but are not limited to, patient medical records, hospital charts if any, clinic charts, laboratory notes, patient's questionnaires, patient's diaries if any, the investigator's files, pharmacy dispensing records and recorded data from automated instruments.

Some specific medical data gathered during routine medical practice visits prior to the participation can be used in screening visit and before informed consent form on the patient best care interest.

All following patient's assessments will be collected via a paper diary and/or paper questionnaire and will be considered as source data:

- IMD compliance: number of instillations/day,
- Contact lens wearing time,
- VAS,
- OSDI questionnaire,
- CLDEQ-8 questionnaire.

The following information should be entered into the patient's medical record:

- Patient's name, date of birth, gender,
- Patient's contact information,
- The date the patient entered the study and patient's number,
- The clinical investigation title and/or the clinical investigation number,
- A statement that informed consent was obtained (including the date) and patient's card was provided to the patient; data protection consent or other country and local patient privacy required documentation for this investigation have been obtained (including the date),

- Date of all patient's visits,
- Investigated disease history:
 - o Diagnosis of DED for each eye,
 - o Date of onset of the diagnosis in each eye (at least months/year),
 - o Previous use of artificial tears,
 - o Contact lens history (type of lens, wearing time during at least the last month per week and day, type of cleaning solution (preserved or not), any history of contact lens intolerance, any other important information regarding contact lens),

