- Ocular and systemic medical and surgery history with diagnosis dates (including dry eye),

For systemic medical history, the information could be collected via patient interview. For ophthalmic medical history of referred patient's, a letter from the referring ophthalmologist is strongly recommended.

- Prior and concomitant medications (list all prescription and non-prescription medications being taken at the time of enrolment and within 3 months before inclusion visit. At each subsequent visit, changes to the list of medications should be recorded),
- Name/initials and signature of the persons who perform assessments,
- Visual acuity values (standard BCVA value with used chart name),
- Slit-lamp examination results with score of ocular signs, conjunctival hyperaemia, corneal and conjunctival fluorescein staining, TBUT,
- Schirmer test results for both eyes,
- Occurrence and status of any AEs,
- Occurrence and status of any DD,
- Review of inclusion/exclusion criteria and patient's status (confirmation of patient eligibility or not, reason for screen failure if applicable),
- Ocular tolerance and performance assessment by Investigator,
- Information on diary dispensation to the patient and instructions correctly provided,
- Information on IMD dispensation, including kit number assignment,
- IMD compliance collected by reviewing patient's diary and interview and checked against returned IMD,
- Information on used/unused IMD by patient,
- The date of the patient exited the study and a notation as to whether the patient completed the study or reason for discontinuation.

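### The unmasked investigator asks the patient for the tolerance rating just before giving two ratings of their own, and at a time that Table 2 contradicts

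*Protocol*

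**What the plan says.** Protocol section 6.4.1.3.4 introduces the patient's four-category tolerance question with the words "The investigator must ask the patient the following question in local language". Section 6.4.1.3.5 has the investigator rate tolerance on the same four categories, and 6.4.1.2.9 has the investigator rate performance. Section 6.4 and footnote 4 to Table 2 keep those two investigator ratings with one assessor across visits. The study is single-arm and open-label (6.1.1), and masking does not apply (6.1.2.3).

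Timing is stated in two places. Table 2 (section 1.4) has the row "Ocular tolerance assessment by the patient ⁽³", whose superscript leads to the note "These questionnaires and VAS must be answered by the patient at the beginning of the visit (before examination". The D15 and D36 lists in section 6.1.6.2 instead put patient tolerance near the end of the visit.

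On source data, section 6.5.1 names the patient assessments that "will be collected via a paper diary and/or paper questionnaire and will be considered as source data": compliance, lens wearing time, VAS, OSDI and CLDEQ-8. Patient tolerance is not among them. The medical-record list in the same section has "Ocular tolerance and performance assessment by Investigator" but no entry for the patient's rating.

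For soothing, section 6.4.1.2.2 says only "Patient will be asked". Section 6.1.3.2 lists it as "Soothing sensation just after (less than 5 minutes) instillation* at D15 and D36", and explains the asterisk as "Patient questionnaire".

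**The concern.** People tend to answer more kindly when the person treating them asks the question. Here that person knows the product, has just examined the patient, and is about to rate the same attribute. In a randomised comparison such a shift might fall equally on both arms. With one arm it goes straight into the reported percentage.

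The conflict over timing adds a second problem. A site that follows footnote 3 collects the rating before fluorescein, the Schirmer strip and the adverse-event discussion. A site that follows the visit list collects it afterwards. The rating could differ for that reason alone, in either direction, and the percentage pooled over about 6 sites would mix two procedures.

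What is at stake is one strand of the evidence for the claim of good ocular tolerance (section 5.1) and, less directly, for the favourable safety profile required in section 7.7.

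**Working it through.** No arithmetic applies. The planned number of patients is blacked out, and no document gives a figure for the effect of who asks. The check sets the texts side by side.

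1. **Who asks.** Section 6.4.1.3.4 names the investigator as the one who asks. That this is done aloud is a fair inference from the verb, not a stated fact. No self-completed form is mentioned for this item.

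2. **When, by Table 2.** At D15 and D36, six rows carry footnote 3: CLDEQ-8, soothing, OSDI, VAS, ocular symptoms and patient tolerance. All six are to be answered before the examination.

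3. **When, by section 6.1.6.2.** The D15 list runs: concomitant treatments, CLDEQ-8, soothing, OSDI, VAS, ocular symptoms, lens wearing time, slit lamp (hyperaemia, TBUT, Oxford), Schirmer, adverse events, device deficiencies, patient tolerance, investigator tolerance, investigator performance. The D36 list keeps this sequence, adding BCVA before the slit lamp and a pregnancy test that may be done at any time. Five of the six footnote 3 items therefore sit before the examination, as the footnote requires. Patient tolerance is the only one that sits after it.

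4. **What follows it.** In both lists the next two entries are the investigator's own tolerance and performance ratings.

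5. **Where it is recorded.** Neither itemised list in 6.5.1 assigns a source to the patient's tolerance rating. This does not prove oral collection, since ocular symptoms throughout the day are also absent from the paper list although labelled a patient questionnaire.

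6. **The same checks on soothing.** No asker and no mode are given in 6.4.1.2.2. It is labelled a patient questionnaire, carries footnote 3, and stands between CLDEQ-8 and OSDI in both visit lists. Its timing is consistent. Only its entry in the 6.5.1 list is missing.

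7. **How it is analysed.** Protocol 7.2.2 and SAP 7.10.4 report both tolerance ratings as frequencies at D15 and D36, with no test. The Wilson interval in SAP 7.1 covers sampling error only, so a shift from the way the question is asked would not show in it.

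**The case against.** **Footnote 3 already treats tolerance as a patient-answered item.** True, and a patient can answer a question that someone else asks, so on mode alone the two texts could coexist. On timing they cannot.

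**The instruction to follow the listed order refers to each eye, so it may govern only the ocular examinations.** This reading is possible. Even so, the list puts one footnote 3 item out of place, and a site working down the page would follow it.

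**A form may exist.** Section 6.5.1 mentions patient questionnaires generally as source documents, appendices are blacked out, and the CRF is not among the documents. This stands as a caution. If a form exists, the wording of 6.4.1.3.4 still needs to agree with it.

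**A clinician's tolerance rating properly draws on what the patient reports.** This stands. A reader might infer that the investigator should rate before learning the patient's answer. The documents do not support that: they nowhere present the two ratings as independent, no agreement analysis is planned, and withholding the answer could make the clinical rating less informative.

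**Soothing.** A reader might infer from the passive wording in 6.4.1.2.2 that the investigator asks for this rating too. The questionnaire label, footnote 3 and its place in the visit lists point the other way.

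**Conclusion.** The point holds for patient-rated ocular tolerance and is minor. The plan states a method prone to interviewer bias, places it directly before the same assessor's own ratings, and contradicts itself on timing. This rests on two assumptions: that being told to ask means a spoken question, and that the investigator who asks is also the one who rates. Delegation could separate the two, but nothing requires it.

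No size can be given. A reader might infer that the bias rivals the sampling error, but nothing in the documents sets its magnitude, and the sample size is not visible.

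The consequence is bounded. The endpoint is descriptive. Section 7.7 does not name it, and adverse events and visual acuity also inform safety. The primary endpoint is a self-questionnaire and is unaffected. For soothing, the only gap is that the way it is collected is not confirmed.

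**What to change.** - **Section 6.4.1.3.4:** replace asking by the investigator with completion by the patient, on the same paper form and at the same time as CLDEQ-8, OSDI and VAS, before the examination as footnote 3 already requires.
- **Section 6.1.6.2:** in the D15 and D36 lists, move patient tolerance up to stand with the other patient questionnaires. The premature discontinuation visit takes its procedures from the final visit (6.1.6.4), so it follows without further change.
- **Section 6.5.1:** add patient tolerance to the paper-source list.
- **Soothing:** confirm self-completion in 6.4.1.2.2 and add the item to the same list. Nothing else needs to change.

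The cost is one added form page and a few wording edits, with no extra visit, staff or analysis. The change reduces interviewer bias and settles the timing. It does not remove the expectation bias of an open-label study without a control arm, and the report should say so when it presents these percentages.
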